**Table 6–2: TEAEs grouped by data driven approach:**

Grouped term	MedDRA search criteria
Pneumonia and Pneumonitis	PT: Lower respiratory tract infection; Lung infection; Pneumonia; Pneumonia pneumococcal; Pneumonia staphylococcal; Lower respiratory tract inflammation; Pneumonitis
Diabetes mellitus and Hyperglycaemia MLG plus	MLG: Hyperglycaemia PT: Diabetes mellitus; Diabetes mellitus inadequate control; Diabetic metabolic decompensation; Type 2 diabetes mellitus; Diabetic ketoacidosis
Renal impairment MLG combo plus	MLG: Laboratory tests related to reduced renal function MLG: Renal impairment PT: Blood urea increased
Rash MLG combo plus	MLG: Rash MLG: Skin erythema PT: Dermatitis
Dizziness MLG plus	MLG: Dizziness PT: Vertigo
Cerebral ischaemia MLG combo plus	MLG: Cerebral infarction and stroke not specified as hemorrhagic or ischemic MLG: Cerebral ischemic infarction and stroke PT: Cerebral ischaemia: Transient ischaemic attack

MLG: MedDRA Labeling Grouping; PT: Preferred Term; HLT: High Level Term

The following tables will be created:

Incidence proportions by worst CTCAE grade: These tables are company standard tables showing the absolute and relative frequencies in each treatment group, by worst CTCAE grade.

- TEAEs by MedDRA (SOC/ HLGT/ HLT/ PT) and worst CTCAE grade,
- Treatment-emergent grouped adverse events by MedDRA labeling grouping (MLG), PT and worst CTCAE grade,
- Treatment-emergent grouped adverse events by data driven grouping, PT and worst CTCAE grade,
- Definition of adverse events MedDRA labeling groupings (MLG),
- Definition of adverse events data driven groupings,
- TEAEs - PTs not covered by MLG or data driven grouping and worst CTCAE grade.

Risk difference, risk ratio, exposure-adjusted rates and incidence rate ratio: These tables show columns for AE grouping, incidence proportion darolutamide, incidence proportion placebo, risk difference with 95% confidence interval (CI), risk ratio with 95% CI, exposure-adjusted incidence rate darolutamide, exposure-adjusted incidence rate placebo, incidence rate ratio with 95% CI.

- Incidence rates and overall risk ratio for grouped terms defined as special topics – double-blind treatment period
- Incidence rates and overall risk ratio for TEAEs by MedDRA SOC, HLGT and HLT – double-blind treatment period. All numbers will be shown on the HLGT and HLT level, not on the SOC level. The SOC is used for sorting only.
- Incidence rates and overall risk ratio for TEAEs by MLG – double-blind treatment period
- Incidence rates and overall risk ratio for TEAEs by data driven grouping – double-blind treatment period

TEAEs over time for common TEAEs (frequency > 5% in any treatment group)

- Interval-specific and cumulative event rates for most common TEAEs by HLGT/HLT grouping – double-blind treatment period
- Interval-specific and cumulative event rates for most common TEAEs by MLG grouping – double-blind treatment period
- Interval-specific and cumulative event rates for most common TEAEs by data driven grouping – double-blind treatment period
- Prevalence over time for most common TEAEs by HLGT/HLT grouping – double-blind treatment period
- Prevalence over time for most common TEAEs by MLG grouping – double-blind treatment period

- Prevalence over time for most common TEAEs by data driven grouping – double-blind treatment period

#### **Adverse events within SOC Cardiac disorders**

The following additional tables for TEAEs by history of cardiac disorders will be created:

- for the subgroup of patients with present medical history in the SOC ‘Cardiac history’,
- for the subgroup of patients without present medical history in the SOC ‘Cardiac history’.

In all tables, results will be shown by treatment group.

Incidence proportions of the TEAEs in the system organ class (SOC) ‘Cardiac disorders’ will be presented by HLGT, HLT, PT and worst CTCAE grade.

Interval specific and cumulative incidence proportions for TEAEs will be presented for the HLGTs Cardiac arrhythmias, Coronary artery disorders, and Heart failures.

In addition, Exposure adjusted treatment-emergent AE (fracture, weight decrease, cardiac disorders, fall) per 100 patient years will be created for the treatment groups:

- Darolutamide – double-blind period
- Darolutamide – double-blind and open-label periods
- Placebo – double-blind period

Below selection will be used:

- Bone fractures: HLT: Fractures and dislocations NEC (without PTs: Joint dislocation, Joint dislocation pathological), HLT: Limb fractures and dislocations (without PT: Radial head dislocation), HLT: Pelvic fractures and dislocations, HLT: Skull fractures, facial bone fractures and dislocations, HLT: Spinal fractures and dislocations (without PT: Dislocation of vertebra), HLT: Thoracic cage fractures and dislocations (without PT: Dislocation of sternum)
- Weight decrease: MLG weight decrease
- Cardiac arrhythmia: HLGT cardiac arrhythmias
- Coronary artery disorders: HLGT coronary artery disorders
- Heart failures: HLGT Heart failures
- Fall: PT Fall and PT Accident

### 6.5.3 Deaths and Serious Adverse events

Serious adverse events (SAE) will be classified using the National Cancer Institute (NCI) Common Terminology Criteria Adverse Event (CTCAE), version 4.03 and MedDRA version 24.0 or most recent version

- TESAEs
- TESAEs leading to study drug withdrawal
- TESAEs leading to dose reduction
- TESAEs leading to drug interruption
- TESAEs leading to dose reduction and/or drug interruption
- Drug-related TESAEs
- Listing of TESAEs
- Listing of non-treatment-emergent SAEs

The incidence of deaths in the study and especially deaths up to 30 days of last dose of study drug will be summarized by each treatment group and cause of death. All deaths up to 30 days of last dose of study drug will be listed by patient with start and stop date of study medication, date of death, and cause of death. All deaths beyond 30 days after last dose of study drug will be displayed in a separate listing.

### 6.5.4 Clinical laboratory data

Descriptive statistics (number of observations, mean, standard deviation, minimum, median and maximum values) will be presented for clinical laboratory tests (hematology, clinical biochemistry and urinalysis), their changes from baseline (including baseline value), and their percent changes from baseline by treatment group at applicable visits.

Hematological and biochemical laboratory values will be graded based on NCI CTCAE version 4.03. CTCAE severity grading for laboratory abnormalities are based on applicable laboratory threshold values outlined in NCI CTCAE v4.03. It should be noted that in the present analysis of those laboratory parameters for which additional clinical information potentially can also influence the toxicity grade, this clinical information is in general not available and only the laboratory measurements are used for grading.

Any additional specific handling of the NCI CTCAE v4.03 toxicity grading assignments will be noted in the footnotes of the corresponding tables as applicable per the data collection in the study.

- In the event of overlapping CTCAE criteria ranges for specific lab tests, the algorithm assigns the worst grade
- If calcium type is not recorded (i.e. only “calcium” is recorded), then grading is done as if the calcium is total calcium. “Calcium corrected” is computed from total

calcium and serum albumin (if  $\leq 4.0$  g/dl) from the same time point based on CTCAE v3.0 guidance. If serum albumin (if  $\leq 4.0$  g/dl) from the same time point is not available or if “calcium, unspecified” was collected then grading is done as if the calcium is “corrected calcium.”

- Results with special characters (such as “>” and “<”) are not graded.

The frequency of laboratory abnormalities regarding hematology, coagulation panel, clinical chemistry, and urinalysis will be tabulated by treatment group. Worst grades for hematological and biochemical toxicities will be calculated according to CTCAE, version 4.03 based on laboratory measurements, and will be summarized by treatment group and NCI CTCAE v4.03 category and worst grade.

Clinical laboratory toxicities during treatment including a period of 30 days after last dose of treatment will be considered as “treatment-emergent.

The last non-missing value before or on the first day of study drug will be retained as “baseline” data. If several assessments are performed on the same day (without timing information) the average of the values will be considered.

Incidence tables (frequency and percentage of patients) as well as tables with change in NCI CTCAE v4.03 worst grade from baseline will be presented as following:

[figure not shown]
- Treatment-emergent hematological and biochemical toxicity.
- Treatment-emergent hematological and biochemical toxicities with incidence rate above 5% in any treatment group.
- Change in worst grade for hematological and biochemical toxicity from baseline.

The laboratory values will be also categorized into low, normal and high according to their reference ranges.

Descriptive statistics will be calculated by treatment group and time interval. 16-week time intervals will be used.

A listing will be provided for all patients possibly fulfilling Hy’s Law criteria, i.e. patients with elevated AST and / or ALT  $> 3xULN$ , alkaline phosphatase  $< 2xULN$  and bilirubin  $\geq 2xULN$ . For possible Hy’s Law cases relevant laboratory data will also be displayed graphically within actual patient profiles (presenting total bilirubin, ALT, AST and ALP values in terms of ULN over time) by treatment group. Below example of Hy’s law plot will be provided for peak total bilirubin vs ALT. If a patient has any total bilirubin  $\geq 2xULN$  then peak bilirubin will be plotted versus the maximum ALT amongst the total bilirubin  $\geq 2xULN$ . Otherwise, peak bilirubin will be plotted versus peak ALT.

Example for Hy’s law plot:

Unscheduled laboratory data will be included in the descriptive tables.

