Methodology: This is a randomised, phase III, multicentre, double-blind, placebo-controlled efficacy and safety study of oral darolutamide in patients with nmCRPC who are at high risk for developing metastatic disease. The study has a design of 2 parallel groups and consists of 2 periods: a study treatment period and a follow-up period. All eligible patients will be randomised to receive darolutamide 600 mg twice daily or placebo in a 2:1 ratio in a double-blind manner. Randomisation will be stratified by PSA doubling time (PSADT; ≤ 6 months vs. > 6 months) and use of osteoclast-targeted therapy (yes vs. no). All patients will visit the study centre at day 1, day 15, day 29, week 16, and every 16 weeks thereafter. CT/MRI and bone scans will be obtained at baseline and every 16 weeks until metastasis. Absence or presence of metastasis will be confirmed at baseline and during the double-blind treatment phase by a blinded independent central reading. Changes identified by central reading must be confirmed with anatomic imaging (CT/MRI or x-ray). Upon central confirmation of metastasis, the patient must be withdrawn from the study treatment and the patient will be followed every 16 weeks for secondary and additional variables (OS, first SSE, pain progression, first prostate cancer-related invasive procedure, initiation of subsequent antineoplastic therapy, initiation of cytotoxic chemotherapy, initiation of opioid use for pain, and changes in ECOG performance status and QoL) until the end of the study by visit or telephone contact. Patients initiating a prohibited therapy before confirmation of the metastasis during the double-blind part should discontinue study treatment and patients will be followed only for survival status until the end of the study. The double-blind part is planned to be continued until the total number of MFS events have been reached at approximately 385 events.		

Once the study results are available, and if they support a positive benefit/risk assessment for darolutamide in the study by judgment of the Sponsor (considering feedback from the study steering committee and/or health authorities), those patients who are on study treatment (darolutamide or placebo) will be offered the opportunity to receive darolutamide through open-label treatment in this study.

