6.1.2.5 Start of open-label treatment visit

Under the conditions outlined in Section 5.9, patients who choose to receive open-label darolutamide will have a start of open-label treatment visit at the time point of study treatment

code unblinding. Those patients who do not choose to continue with open-label darolutamide treatment, will have an end-of-study treatment visit at this point of time (see Section 6.1.2.6).

The following procedures will be performed during the start of open-label treatment visit:

- QoL:
 - BPI-SF and EORTC-QLQ-PR25: all patients
 - FACT-P and EQ-5D-3L: placebo patients crossing over to open-label darolutamide treatment
 - PCS-subscale of FACT-P: patients in the darolutamide arm continuing open-label darolutamide treatment

If the end of the double-blind treatment period occurs less than 16 weeks from the start of study treatment, the EQ-5D-3L assessment is required in the first 16 weeks of open-label darolutamide treatment.

- Physical examination including weight
- A 12-lead ECG in a supine position after at least 10 minutes rest. An ECG with a QTcF > 500 ms should be confirmed by a second ECG taken 1-2 hours later. 12-lead ECG will be performed only at the start of open-label visit. ECG is not required on subsequent visits during the open-label darolutamide treatment.
- BP and HR (unless recorded by ECG) in a supine position after at least 10 minutes rest
- Laboratory safety assessments (haematology, chemistry and urinalysis) and PSA
- Chest, abdomen and pelvic CT/MRI **and** bone scan. Scans are acceptable if performed within 42 days prior to the start of open-label treatment visit. Imaging will be conducted every 16 weeks (± 7 days) during the open-label darolutamide treatment after the start of open-label treatment visit. Central confirmation of local imaging is not required during the open-label darolutamide treatment.
- A blood (plasma) sample for tumour-related biomarker analysis unless precluded by local guidelines, e.g. IEC/IRB or regulatory authorities (see Section 6.5)
- ECOG performance status
- Date of first SSE
- Date of first prostate cancer-related invasive procedure
- Status of survival
- Current medical condition, AEs and concomitant treatments
- Collection of pain diary and dispensing a new pain diary

- Return of all remaining study drugs and study drug containers and drug accountability performed. Study drug for the open-label treatment phase will be dispensed for 16 weeks.

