### **6. Statistical Methodology**

The statistical analyses will be descriptive. Summaries will be provided for both treatment groups, darolutamide and placebo.

For disposition tables, concomitant medications, concurrent procedures, study-drug exposure tables and adverse events tables, the patients who switched from placebo to darolutamide during the open-label period will be displayed. These following treatment groups will be shown: darolutamide total (double-blind and open-label periods), darolutamide double-blind period, placebo double-blind period, placebo-darolutamide cross-over patients.

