## 6.5 Safety

All data including the open-label period will be summarized.

For patients randomized to darolutamide, safety events will be displayed separately for:

- the double-blind period

- the double-blind and open-label periods (total)

For patients randomized to placebo, safety events will be displayed separately for:

- the double-blind period
- the open-label period after cross-over to darolutamide treatment

The double-blind period of the study only will be considered for risk difference, risk ratio, interval-specific incidence and prevalence.

If the start date of the AE is missing then the event will be considered occurring during the double-blind period.

No formal statistical tests will be done for the safety endpoints. All analyses for safety will be performed in the SAF population.

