#### 4.5 Data Rules

Generally, for each date stored in the database, a set of organizational variables will be derived in order to describe the temporal context of that date in the specific study: phase of treatment (pre, during or post study treatment), day relative to the start of study treatment, day relative to the end of study treatment.

Additional contextual variables may be created in analysis datasets.

Refer to Section 4.3 for handling of missing data, as well as to Section 6, for specific endpoints data rules, for example censoring patients or definition of treatment-emergent adverse events (TEAEs).

All derived variables will be stored in analyses data sets (ADS) created by the statistician and / or the statistical analyst.

Since differences may occur between the values of the stratification variables entered by the investigator at the time of randomization (IVRS) and those collected on the CRF, the analysis will be performed using both assignments to the strata. However, the primary stratified analyses for the efficacy endpoints will be based on the information collected in the IVRS whereas stratification information entered in the CRF (considered the 'true' information) will be used for sensitivity analyses. In rare circumstances, if CRF data cannot be documented, then IVRS data will be used.

Baseline data for stratification will be taken from the last non-missing observation on or before the randomization date.

Baseline data for demographics and characteristics, PRO questionnaires and safety will be taken from the last non-missing observation on or before the first day of study drug intake.

Reported outcome questionnaires dates of completion were not collected therefore the dates of corresponding visit will be used for analyses.

Unscheduled visits will be considered in analyses, excepted for analyses of health-related QoL.

A data cut-off date for the final and the interim efficacy analyses will be chosen.

Time to event variables values will be displayed in months. Months will be calculated dividing days by 30.44.

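### SAP Supplement 7 sets one laboratory baseline and no stated column for crossover patients, so their change on darolutamide cannot be separated from change on placebo

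*SAP*

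**What the plan says.** Supplement 7 section 6.5.4 defines the laboratory baseline once: "The last non-missing value before or on the first day of study drug will be retained as" baseline. The main SAP v4.2, section 4.5, has the same rule; baseline for "safety will be taken from the last non-missing observation on or before the first day of study drug intake". Neither text has a separate rule for patients who move from placebo to darolutamide.

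Study treatment covers both arms. The protocol (Synopsis and section 5.9) offers open-label darolutamide to "those patients who are on study treatment (darolutamide or placebo"). A placebo patient's first day of study drug is therefore naturally read as his first placebo day.

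Open-label data are in scope. Supplement 7 section 6.5 opens with "All data including the open-label period will be summarized". Protocol Table 4 schedules laboratory safety tests for crossover patients every 16 weeks and at the end-of-study treatment visit. Protocol section 6.1.2.5 also lists "Laboratory safety assessments (haematology, chemistry and urinalysis) and PSA" at the start of open-label treatment visit.

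Three places bear on the display columns:

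- Supplement 7 section 6 gives the default: "Summaries will be provided for both treatment groups, darolutamide and placebo". It then lists the tables with a crossover group: "For disposition tables, concomitant medications, concurrent procedures, study-drug exposure tables and adverse events tables, the patients who switched from placebo to darolutamide" are to be displayed. Laboratory tables are not in that list.
- Supplement 7 section 6.5 shows safety events of placebo patients separately for the double-blind period and for "the open-label period after cross-over to darolutamide treatment". It does not say whether safety events include laboratory changes.
- Supplement 7 section 5 adopts the main SAP analysis sets. Under main SAP section 5, a patient stays in the placebo arm for safety only if he never took darolutamide.

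Section 6.5.4 itself says only that results are shown by treatment group.

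**The concern.** The main SAP v4.2 served an analysis at the end of the double-blind part, where one pre-treatment baseline is the usual choice. Supplement 7 carries that rule into a report that adds open-label data. The crossover group then has two treatment periods but one reference value, taken before the first.

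Drift from disease, ageing or androgen deprivation during the placebo period can therefore be mixed with any effect of first darolutamide exposure. The mixing can go either way. A grade shift acquired on placebo that persists is counted again after crossover. A value that improved on placebo and then fell back on darolutamide can look like no change.

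At stake is whether a reader of the addendum can learn anything about laboratory change in men newly exposed to darolutamide after a placebo period.

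**Working it through.** The plan states no figure to reproduce here. The check is to trace the rules through each permitted display, then illustrate the possible size.

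**Step 1. Age of the baseline at crossover (planned dates only).** Protocol section 8.14 plans a start in Q3 2014, and section 7.1 assumes 40 months of accrual. Forty months from July to September 2014 ends between November 2017 and January 2018. SAP v4.2 is dated 20 September 2018, and protocol section 7 requires the SAP to be approved before the code is opened. If the planned dates held and v4.2 preceded unblinding, the last patients randomised would have been on study for at least about 8 months at crossover (January to September 2018), and the first for about 4 years (Q3 2014 to September 2018). This is an estimate from planned dates, not a reported duration.

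**Step 2. Trace the three displays the text allows.**

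- *A. Separate post-crossover column* (Supplement 7 section 6.5, if safety events include laboratory data). Open-label values are compared with the pre-placebo value. Change that arose on placebo appears in a darolutamide column.
- *B. Safety-set rule read literally* (main SAP section 5). The crossover patient's whole record, placebo period included, goes under darolutamide. Shifts on placebo are counted there whether or not they persist, so the carry-over is at least as large as in A.
- *C. Two groups as randomised* (Supplement 7 section 6 default). Open-label values stay under placebo. The error reverses: values on darolutamide are counted as placebo.

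In none of the three is change since the first darolutamide dose shown for these patients.

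**Step 3. Which displays use the baseline.**

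- Depend on it: change from baseline, percent change from baseline, and change in worst grade from baseline.
- Do not depend on it: treatment-emergent toxicity (defined by a time window ending 30 days after last dose), the low/normal/high categories, and the Hy's Law listing and plots.

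**Step 4. Illustration for display A.** The documents give neither laboratory rates nor the number of crossover patients, so the inputs are assumptions. Let p be the share already at least one grade worse than on day 1 when darolutamide starts, with the worsening persisting. Let q be the share newly worse on darolutamide. Take the two as independent and ignore patients who improved on placebo.

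Shown with the day-1 baseline: 1 − (1 − p)(1 − q). Shown with a baseline at the start of open-label treatment: q.

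| p (assumed) | q (assumed) | Day-1 baseline | Open-label baseline | Excess |
|---|---|---|---|---|
| 5% | 5% | 1 − 0.95 × 0.95 = 9.75% | 5% | 4.75 points |
| 10% | 5% | 1 − 0.90 × 0.95 = 14.5% | 5% | 9.5 points |
| 20% | 5% | 1 − 0.80 × 0.95 = 24% | 5% | 19 points |
| 30% | 5% | 1 − 0.70 × 0.95 = 33.5% | 5% | 28.5 points |

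For mean changes, an assumed drift of d standard deviations a year over t years on placebo carries over d × t. For example, 0.2 × 1.5 = 0.3 standard deviations.

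**The case against.** The strongest reply is that no passage says placebo-period changes are presented as darolutamide changes. Laboratory tables are missing from the section 6 list of tables with a crossover group, the default is two groups, and section 6.5.4 adds nothing. If groups are as randomised, nothing from crossover patients is labelled as on darolutamide. This stands. A reader might infer that the plan reports placebo drift as a darolutamide effect, but that holds only under displays A and B, and the text does not choose between them and C.

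A second reply is that one pre-study baseline is a legitimate convention for cumulative change since entry. That is fair, and it is a reason to keep that baseline in the other columns. It does not answer the question the crossover group raises.

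Third, Supplement 7 is based on a Supplemental 4 SAP and lists a Supplemental 5. Main SAP section 4.3 also leaves treatment phases and periods to programming and an operational manual. A period-specific rule could exist in any of these. The point can therefore claim only that the supplied text does not state one.

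Fourth, the tables are descriptive, no formal safety tests are planned, and risk differences and ratios are restricted to double-blind data. This also stands and limits the weight of the point.

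**Conclusion.** The point holds as a gap with two linked parts. Section 6.5.4 fixes a single baseline that, for crossover patients, predates placebo. It also leaves open which column their open-label laboratory values enter. Depending on the column, change on placebo is carried into darolutamide results or values on darolutamide are counted as placebo. Under no reading does the stated rule isolate laboratory change after first darolutamide exposure in these patients.

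The baseline problem is confined to the change, percent-change and worst-grade shift displays. No hypothesis test, error rate, power figure or treatment-emergent incidence definition is affected. A reader might take the percentages in the illustration as an estimate of the error; they are not, because p and q are assumed. The conclusion also rests on reading study drug as including placebo, and on no other document supplying a crossover baseline.

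This deserves correction before the addendum tables are programmed, because the missing rule decides what those tables mean and the value needed is already scheduled.

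**What to change.** In Supplement 7 section 6.5.4, add two statements:

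1. Laboratory tables use the same groups and periods as the adverse-event tables: darolutamide double-blind, darolutamide total, placebo double-blind, and placebo-darolutamide crossover.
2. For the crossover column, baseline is the last non-missing value on or before the first open-label darolutamide dose. All other columns keep the existing baseline.

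The sample at the start of open-label treatment visit would normally supply the crossover baseline; if it is missing, the rule falls back to the latest earlier value. The cost is a short addition to the text, a second baseline flag and slightly more programming. No new data are needed and no clinical rule changes.
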